 State of Illinois Department or Agency, please specify :  Other, please specify :
4C. Sponsor-assigned grant number, if known: 1U01AI169469 - 01
4D. A complete copy of the funding proposal or contract is attached.  Attached, please specify title : COVID-19 Treatment Cascade Optimization Study
4E. Funding Agency Official To Be Notified of IRB Approval (if Applicable) Name: Program Officer TBD- [name], Grants Management Specialist Agency: NIAID/NIH E-mail: [contact] [contact]

Section 5. CONFLICTS OF INTEREST

Please indicate below whether any investigators or members of their immediate families have any of the following. If the answer to any of the following items is yes, please submit the University of Illinois approved conflict management plan. If you have any questions about conflicts of interest, contact [contact].

5A. Financial interest or fiduciary relationship with the research sponsor (e.g. investigator is a consultant for the research sponsor).  Yes  No
5B. Financial interest or fiduciary relationship that is related to the research (e.g. investigator owns a startup company, and the intellectual property developed in this protocol may be useful to the company).  Yes  No
5C. Two or more members of the same family are acting as research team members on this protocol.  Yes  No

Section 6. SUMMARY & PURPOSE OF RESEARCH

6A. In lay language, briefly summarize the objective and significance of the research. COVID-19 has impacted the health and social fabric of individuals and families living across the United States; and it has disproportionately affected people living in urban communities with co-morbidities, those working in high-risk settings, refusing or unable to adhere to CDC guidelines, and more. Social determinants of health (SDH), such as stigma, racial discrimination, xenophobia, incarceration, and poverty have been associated with increased exposure to COVID-19 and increased deaths. Marginalized communities, defined as low-income and racial/ethnic minority neighborhoods, where residents experience increased barriers (e.g., inadequate housing, high-risk jobs) to prevention and treatment, bear disproportionately higher rates of co-morbidities associated with more severe cases of COVID-19. While effective and potent vaccines are becoming more available, it will take time to reach herd immunity and it is unclear how long newly-developed vaccines provide protection and how effective they are against emerging variants. Therefore, prevention methods recommended by the Centers for Disease Control and Prevention (CDC) – i.e., testing, hand-washing, social distancing, contact tracing, vaccination, and quarantine -- are essential to reduce the rates of COVID-19 in marginalized

communities. Research about COVID-19 testing and vaccine uptake in these communities must occur in real time and it must account for the fast-changing landscape of the pandemic, including the impact of vaccine availability on testing uptake. Two cost-effective, evidence-based, and culturally appropriate interventions have been effective in engaging people in HIV prevention and treatment – these can be adapted and tested to help address COVID-19 prevention needs. Specifically, Navigation Services (NS) have been shown to increase HIV testing and adherence to treatment while addressing structural barriers that deter treatment engagement in high-risk communities; and Brief Counseling (BC) has been shown to increase HIV treatment engagement.

[name] has an ongoing grant (3 R01 MD010629-04S2 – From here after referred to as COVID-19 NJ Study)) which aims to optimize an adaptive intervention to increase testing, and access to treatment and to prevention of COVID-19 infections in a medically or socially vulnerable sample of 670 people in Essex County, NJ. The COVID-19 NJ Study is under the North Jersey Community Research Initiative (NJCRI) IRB oversight, entitled *Optimization of a new adaptive intervention to increase COVID-19 testing among people at high risk in an urban community*, Protocol #: CWCVIDSUPP-UIUC-NJCRI 102497-18274-267805 and has a reliance agreement in place with UIUC.

The new project, COVID-19 IL Study, which is being reviewed by the UIUC IRB, proposes to expand the NJ project to include a sample of 548 people in Illinois. We will use the same protocol that was used in NJ in addition to de-identified data that is currently being collected by the COVID-19 NJ Study. The final study sample will include 670 people from NJ and 548 people from IL for a total of 1,218. Data from the 670 people in NJ will be treated as secondary data and data from the 548 people in IL will be treated as primary data under the COVID-19 IL Study IRB protocol.

The COVID-19 IL Study will use Multiphase Optimization Strategy (MOST) and Community-Based Participatory Research (CBPR) principles and best practices to help facilitate recruitment and to make results readily available to the population. Illinois participants will be randomized two separate times: First, into two distinct groups to receive: (1) navigation services or (2) informational brochure. We aim to help participants to get a COVID-19 test between baseline and the first follow-up (7 days post baseline). Second, after completing the first follow-up, participants are then randomized again to continue with the original intervention or switch to a new one. We then collect data at 2; 5; 12; and 24 weeks post-baseline follow-ups.

The COVID-19 IL Study specific aims include:

Primary Aims: (1) To examine the effectiveness of an adaptive intervention to increase COVID-19 testing and adherence to CDC-recommendations of preventive behaviors – social distancing, hand-washing, mask-wearing, vaccination- on comparable but distinct samples. We will control for baseline, time, demographics and COVID risk; (2) To examine the immediate and medium-term impact of the adaptive intervention on COVID testing and adherence to recommendations by collecting follow up data at 2,5,12, and 24 weeks post baseline.

Implementation aim: To collect intervention implementation data (context, cost, barriers, lessons learned) and develop implementation materials (facilitator training, intervention manual, treatment fidelity measure).

6B. Indicate if your research includes any of the following:

- Secondary data (use of data collected for purposes other than the current research project) De-identified collected data by the COVID-19 NJ Study, described in final paragraph of 6A and COVID-19 testing results collected from CBHC.
- Data collected internationally (include [International Research Form](#))
- Translated documents (include [Certificate of Translation Form](#) and translated documents)
- Research activities will take place at Carle (include documentation (email or letter) from Carle stating that the review of your [Research Services Request Form](#) is complete)

6C. Letters of support from outside institutions or entities that are allowing recruitment, research, or record access at their site(s) are attached. Yes Not Applicable

Letters of support from NJCRI and CBHC are in the NIH proposal (p.129- 132 of the attached proposal PDF)

Section 7. PROCEDURES

7A. Select all research methods and/or data sources that apply.

- Surveys or questionnaires, *select all that apply:* Paper Telephone Online
- Interviews
- Focus groups ("Critical Dialogue" Sessions)
- Field work or ethnography
- Standardized written, oral, or visual tests
- Taste or smell testing
- Intervention or experimental manipulation
- Exercise and muscular strength testing
- Noninvasive procedures to collect biological specimens (e.g., hair and nail clippings, saliva, etc.)
- Noninvasive procedures to collect physiological data (e.g., physical sensors, electrocardiography, etc.)
- Procedures involving radiation
- Recording audio and/or video and/or taking photographs
- Recording other imaging
- Materials that have already been collected or already exist, *specify source of data:* De-identified data collected at another project that is led by the PI, [name] in New Jersey at NJCRI using the same protocol will be analyzed.
- [HIPAA-protected data](#)

 FERPA-protected data  GDPR-protected data  Other, please specify:
7B. List all testing instruments, surveys, interview guides, etc. that will be used in this research. Eligibility Screener Enrollment Baseline Survey Follow up 1 to 4 Survey Brochures Drafts or final copies of all research materials are attached.  Yes
7C. List approximate study dates. 03/10/2022- 12/31/2023
7D. What is the duration of participants' involvement? 6 months
7E. How many times will participants engage in research activities? Participation will complete 1 baseline and 4 follow up assessments. Those randomized to Navigation Services will complete at least one phone session of up to 30 minutes on the phone. They may request as many navigation sessions as they need. Those randomized to Brief Counseling will complete one 15 minutes long phone session. Those randomized to Critical Dialogue will complete one 60 minutes long session in-person or online.
7F. Narratively describe the research procedures in the order in which they will be conducted. This study will track participants for six months in order to capture changes over time in COVID-19 testing and adherence to public health recommendations. We will use a Sequential, Multiple Assignment Randomized Trial (SMART) with a total sample of 1,218 COVID-19 medically and socially vulnerable people, 548 of which will be primary data collection and 670 will be secondary data. All participants will receive at least one intervention and no more than two interventions, depending upon randomization. After having been determined eligible through a brief phone screening process, participants will be invited to provide consent to participate and complete the baseline online. Those interested in the study will call the study phone. A research assistant or outreach worker will complete the phone screening with the participant to determine eligibility. If eligible, they will be asked to provide alternative forms of contact in case we are unable to reach them. The staff will explain that they will let the alternative contact know we are looking for the participant because it is time for them to complete their follow-up survey. Participants may choose not to provide any contacts. Those who complete the baseline will then be randomized by Redcap to either receive Navigation Services or Brochure: Navigation Services (NS): Navigation services include assessment and support with service referrals. Each participant randomized to this intervention will meet with a peer navigator in person or on Zoom Conferencing for 30 minutes to go over results from their social and health needs assessment that is retrieved from the base-line survey. The navigator shares information about COVID-19, answers questions about testing, and makes referrals to other needed services (e.g., housing, food, mental health, employment, transportation, primary care). The participant is then referred to the testing site and encouraged to get tested as soon as possible. The peer navigator calls participants who consent to follow up, find out what services they received, and what services they still need. The frequency of sessions is decided between the participant and the navigator. The peer navigator can then make new

referrals and help participants address identified barriers to services. All referrals and referral outcomes will be tracked and entered into the project database.

Brochure: This intervention includes two different electronic brochures: One with information about COVID-19 testing (including where and how to get tested), and one with information about COVID-19 prevention and treatment. The brochures will be updated in real time to reflect the most recent CDC public health recommendations. Brochures will be e-mailed to all participants automatically by Redcap upon randomization and one week after they complete the baseline.

Once randomized, all participants will receive the brochure that includes information about testing at CBHC. Navigators will speak to their clients about testing, and, if the participant is interested, they can schedule the COVID-19 test for participants. Note participants will not be pressured to test. They will simply receive the information on how to do so and we will ask them to do it prior to completing their follow-up, if they choose to get tested. Home tests will not be accepted for the purposes of the study.

One week post-baseline, participants will complete the first follow-up survey. Those who received a COVID-19 test between baseline and Follow-up 1 will be randomized to either continue to receive their original intervention (NS or Brochure) or to switch to receive Brief Counseling. Those who fail to get a COVID-19 test between baseline and first follow-up will be randomized to continue the original intervention (NS or Brochure) or switch to receive Critical Dialogue:

Brief Counseling (BC): Brief Counseling is a 15-minute post-COVID-19 test session delivered by a trained licensed clinician in person or via Zoom Conferencing. In the session, the clinician shares the test results and offers recommendations and information about COVID-19 treatment and prevention. Clinicians will be members of the research team and employed by CBHC.

Critical Dialogue (CD): Critical Dialogue includes one two-hour “focus group” session facilitated in person or online by a trained licensed facilitator. Group critical dialogue is prompted by thematic images developed by the Newark Community Collaborative Board (NCCB) to foster a deeper understanding of how systematic stigma, feelings of rage as victims of discrimination, and/or apathy may impact participants’ beliefs and behaviors related to COVID-19 and empower participants to make critical choices to protect their health and the health of their communities.

COVID-19 test procedures and HIPPA protected data collection and sharing: Enrolled participants interested in getting tested for COVID-19 will either come into CBHC or meet the trained outreach worker to collect the sample. CBHC holds a Clinical Laboratory Improvement Amendment (CLIA) Certificate of Waiver and uses the Lumira Dx SARS-CoV-2 Ag Test (see attached instruction manual). The outreach worker will be using N-95 mask and gloves. Participants are asked to collect their own nasal sample and hand it over to the outreach worker who processes it. It takes 15 minutes to obtain the test results and participants are informed immediately. They receive the study brochure that provides

information about how to prevent COVID-19 and what to do if tested positive. As soon as the results come out, the outreach worker logs into Redcap and records the test completion date and results.

In cases where the sample is collected outside of CBHC, the participant will be asked to collect the sample following the instructions, place it into a plastic bag, and hand it to the outreach worker. The collection bag will have the participants' study code number written on it and it is transported in a cooler container back to CBHC. Once the sample is processed, the outreach worker calls the participant to provide the test results and logs the information in Redcap. They receive the brochure when they turn in the sample.

With participants' permission, we will share the COVID-19 test results and some identifying information (e.g., zip codes) with the Duke Clinical Research Institute (DCRI). HIPPA data will be downloaded from Redcap automatically including only data that was authorized by participants to be shared with the CDCC. This will be a CVS file which is downloaded into Box Health. The file is then uploaded weekly into the Duke data portal (see attached CDCC Data guidance pdf).

Participants who report not getting tested in follow-up 3 will be invited to participate in a Critical Dialogue session before completing Follow-up 4.

[figure not shown]
All participants will be asked to complete follow ups 4 and 5. We will collect screening data via phone, and in-person baseline assessment, and follow- ups at 2, 5, 12 and 24 weeks follow-ups. Participants will be encouraged to complete the surveys online, using their phones, a tablet, or computer. They can also request to meet the outreach workers at CBHC or a public place to complete the data collection using a study tablet, as long as they agree to adhere to the most current public health recommendations (e.g., social distancing).

After each assessment, participants will be asked to provide extensive locator information, on forms used for the parent study, including formal and informal contacts who can reach the participant in a variety of contingencies. During the follow-up period, outreach workers will maintain monthly contact with participants by mail or phone and will update locator information. Randomization and data collection will be done online using Redcap. We will voice record all Critical Dialogue sessions with participants' consent and will randomly select 20% of them for analysis.

The research team will randomly select 35 participants at each site who decline to be tested for COVID-19 and invite each of them to complete an in-depth, one-on-one, qualitative interview lasting about 30 minutes. After providing written informed consent, participants will be assigned code names and asked to talk about their experiences with the intervention, barriers they faced to testing and adhering to public health guidelines, and their ideas about how to address these barriers. The interviews will be digitally voice-recorded, transcribed and entered into Atlas.ti for storage and analysis. Transcripts and Atlas.ti files will be identified only by code name.

Additionally, data from the COVID-19 NJ Study will be analyzed. These data include the exact same surveys as the data being collected in Illinois. The data is being collected under NJCRI's IRB number. UIUC deferred to the NJCRI IRB because all the NJ data is being collected there. The NJ data will be de-identified and shared electronically by the NJ research assistant using Box. The NJ data will then be merged with the Illinois data for analysis.

The figure below illustrates the study design:

COVID-19 Testing

Section 8. PERFORMANCE SITES TO INCLUDE INTERNATIONAL, SCHOOL, AND COLLABORATIVE STUDIES

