codenames only and kept in password-protected devices/servers, separate from identifying information and available only to project staff. This helps to ensure that no identifying information will be disclosed in the unlikely event that computerized data are stolen or otherwise seen by unauthorized persons.) All identifying electronic data will be destroyed immediately after data analysis is completed. Signed consent forms will be kept for 3 years after study completion. Deidentified electronic data will be kept indefinitely. Participants may ask at any time to have recordings of their interview destroyed by calling/e-mailing one of the Principal Investigators at the numbers provided in the informed consent forms. Voice recordings will be kept indefinitely for data analysis. However, if we have reason to believe that any of these recordings contain information that can put any of our participants in danger of being harmed, we will destroy the recording.

Our interviewers are trained to watch participants carefully and will stop questioning if an individual appears uneasy. At every interview, participants will be informed that they may ask the interviewer to stop if they are feeling uncomfortable. Referrals to counselors are available if participants wish and trained clinical counselors are available at CHBC in the event that someone may need immediate assistance, whether it is during data collection or during the intervention sessions. [name], [name], and [name] will be available by phone at all times in case an emergency occurs. Clinical emergencies will be handled by treatment teams of experienced staff at CBCH under the leadership of [name]. Appropriate assessments will be conducted; treatment options will be recommended and followed through as necessary. CBHC routinely provides services to individuals with mental health and substance use disorders is fully equipped to address any potential emergencies either themselves or via referrals.

Finally, the research team and the clinical team will engage in weekly project meetings to discuss the progress of the study and identify, discuss, and address any potential issues.

Section 10. INCLUSION/EXCLUSION

10A. List specific criteria for inclusion and exclusion of subjects in the study, including treatment and control groups.

Criteria for inclusion include:

- 18 years of age or older
- having high risk to contract COVID-19 or develop related complications
- able to Speak English at the 7th grade level

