- able and willing to provide informed consent

10B. Explain how the inclusion/exclusion criteria will be assessed and by whom. If special expertise is required to evaluate screening responses or data, list who will make this evaluation and describe their training and experience.

A trained outreach worker will conduct a brief phone screening using the attached brief phone screening to obtain self-reported eligibility information including risk for contracting COVID-19 and developing related complications.

10C. Drafts or final copies of all screening materials are attached. Yes Not Applicable

10D. Describe procedures to assure equitable selection of subjects. Justify the use of the groups marked in Section 9B. Selection criteria that target one sex, race, or ethnic group require a clear scientific rationale.

The proposed study does not include children because the adaptive intervention will focus on adult behaviors and it would not be appropriate to include children. The staff has been trained to work with adults and the parent grant only included individuals over the age of 18. Finally, the supplement includes several interview questions regarding social determinants of health that children would not be able to answer. Recruitment will be open to residents of both Essex County, NJ and St. Clair County, IL, but given the location of the study sites, we expect that the vast majority of participants will come from the Newark, NJ and East St. Louis, IL areas. As such, we estimate that our sample will approximate the demographics of Newark and East St. Louis in terms of sex/gender, race and ethnicity. Because of this, we anticipate that Black participants will be overrepresented in our sample.

Section 11. RECRUITMENT

11A. Select all recruitment procedures that will be used.

- Student subject pool, *please specify*:
- Email distribution
- MTurk, Qualtrics Panel, or similar online population, *please specify*:
- US Mail
- Flyers/brochures
- Website ad, online announcement (e.g. eWeek), or other online recruitment, *please specify*:
- Newspaper ad
- Verbal announcement
- Other, *please specify*: Street outreach
- Not applicable (secondary data only)

11B. Drafts or final copies of all recruitment materials (including verbal scripts) are attached.

- Yes Not Applicable

11C. For each group of participants, describe the details of the recruitment process.

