COVID-19 Treatment Cascade Optimization Study

NCT05305443

Statistical Analysis Plan

3/30/2022

Statistical Analysis Plan

Data analysis: Aim 1. We will estimate the (1) differences in the effects of first-stage interventions (NS vs brochure), (2) differences in the effects of second-stage interventions (BC vs NS among those who complete testing and referral vs CD among testing decliners), and (3) differences in the effects of selected adaptive interventions on acceptance of testing and adherence to IL recommendations. For differences between NS and brochure, cross-tabulations of the interventions with each outcome will be generated, and crude odds ratios comparing the two will be calculated. For the effects of second-stage and third-stage interventions, we will perform a similar analysis as that for the first-stage interventions but on corresponding subsets as indicated in the specific comparison groups. The estimation of effects of embedded adaptive interventions will use weighted and replicated estimation techniques. Under these procedures, the data set will be restructured wherein an individual's outcome will be replicated in the data set depending on the number of adaptive interventions consistent with this outcome. Since randomization at both stages is based on equal probabilities, weighing is not necessary. The restructuring of the data set as described allows the utilization of standard statistical software for parameter estimation and hypothesis testing. A generalized linear model using logistic regression will be performed where estimation of model parameters will be done using generalized estimating equations due to the presence of replicated subjects. We will then use tests of contrasts to compare selected adaptive interventions. The analysis of the adaptive interventions will be done using PROC GENMOD in SAS. To adjust for baseline characteristics and test for their moderating effects, we will incorporate these terms and their interactions with first-stage, second-stage, and adaptive interventions in their respective models. Only the baseline characteristics will be used for adjustment, as outcomes of the first-stage intervention are biased if incorporated into this model. Odds ratios, 95% CI, and Wald's test for the effect of interventions and covariates will be obtained from these results. Sex/gender and race/ ethnicity will be among these covariates that we will consider for adjustment and moderation analysis.

Interim analyses

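### Vaccination is an adherence outcome with no definition and no baseline restriction, so the SAP's crude odds ratio is pulled toward 1 if it is scored as ever vaccinated

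*Protocol*

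**What the plan says.** Protocol section 6A, Primary Aim 1, names the preventive behaviours as "social distancing, hand-washing, mask-wearing, vaccination". The next sentence adds "We will control for baseline, time, demographics and COVID risk". It does not say which baseline variables are meant.

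Section 10A lists four inclusion criteria: "18 years of age or older", "having high risk to contract COVID-19 or develop related complications", English ability, and "able and willing to provide informed consent". None concerns vaccination status. Section 7C gives the study dates as "03/10/2022- 12/31/2023", and section 6A says "While effective and potent vaccines are becoming more available", so some participants should be expected to arrive already vaccinated.

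The SAP (Data analysis: Aim 1) does not name vaccination. It treats adherence to Illinois recommendations as an outcome and states: "For differences between NS and brochure, cross-tabulations of the interventions with each outcome will be generated". Crude odds ratios follow, and a similar analysis is planned on subsets for the later stages. Separate models bring in baseline characteristics and their interactions with intervention. Sex/gender and race/ethnicity are the only covariates named there.

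**The concern.** Distancing, hand-washing and mask-wearing can rise or fall after randomisation. Receipt of a given vaccine dose cannot be reversed. If the outcome is whether a participant has ever had that dose, those who had it before baseline are successes whichever arm they enter. They carry no information about the intervention, yet they add equally to both arms of a crude comparison.

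At stake is the vaccination part of Primary Aim 1. A real effect among people who could still be vaccinated could appear in the crude odds ratio as small or absent.

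**Working it through.** **Inputs from the documents.** Total sample 670 + 548 = 1,218 (Protocol section 6A). Randomisation is with equal probabilities (SAP), so 1,218 / 2 = 609 per first-stage arm. The 95% confidence intervals imply two-sided 5%. The documents give no power calculation, vaccination rate or effect size, so there is no stated figure to reproduce.

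**Assumptions.** The outcome is ever vaccinated; uptake among the unvaccinated is c = 10% with brochure and t = 20% with navigation; there is no dropout; the share vaccinated at baseline, v, is 40%, 60% or 80%.

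**Formulas.**
- Proportions in everyone randomised: p_c = v + (1 − v)c and p_t = v + (1 − v)t.
- Risk difference: p_t − p_c = (1 − v)(t − c), so it shrinks by exactly 1 − v.
- Standard error of the log odds ratio with n per arm: SE = √[1/(n·p_c(1 − p_c)) + 1/(n·p_t(1 − p_t))].
- Power ≈ Φ(log OR / SE − 1.96).
- In those unvaccinated at baseline, the same formulas apply with c, t and n(1 − v) per arm.

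**Worked case, v = 60%.** p_c = 0.6 + 0.4 × 0.10 = 0.64 and p_t = 0.6 + 0.4 × 0.20 = 0.68. OR = (0.68/0.32)/(0.64/0.36) = 1.20; log OR = 0.178; SE = 0.121; z = 1.47; power = Φ(−0.49) = 31%. Restricted: 609 × 0.4 ≈ 244 per arm; OR = (0.20/0.80)/(0.10/0.90) = 2.25; log OR = 0.811; SE = 0.267; z = 3.04; power = Φ(1.08) = 86%.

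| v | All randomised | Risk difference | Crude OR | Power, crude | Unvaccinated per arm | OR, restricted | Power, restricted |
|---|---|---|---|---|---|---|---|
| 40% | 52% vs 46% | 0.06 | 1.27 | 55% | 365 | 2.25 | 96% |
| 60% | 68% vs 64% | 0.04 | 1.20 | 31% | 244 | 2.25 | 86% |
| 80% | 84% vs 82% | 0.02 | 1.15 | 15% | 122 | 2.25 | 57% |

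At v = 20% the crude odds ratio is already down to 1.45. With the Illinois sample alone (548 / 2 = 274 per arm) and v = 60%, power is 17% crude and 53% restricted.

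**Would baseline adjustment help?** I fitted logistic models to the v = 60% case with counts rounded to whole people: per arm, 365 vaccinated and 244 unvaccinated, of whom 24 and 49 become vaccinated.
- Intervention only: OR 1.20.
- Intervention plus baseline vaccination: log OR 0.834, SE 0.268, OR 2.30.
- Unvaccinated only: log OR 0.834, SE 0.268, OR 2.30.

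Rounding explains 2.30 rather than 2.25. The last two fits agree because, once the covariate is in the model, the already vaccinated contribute nothing to the intervention effect. The covariate's own coefficient diverges (about 28, SE about 13,000), since everyone vaccinated at baseline is a success. Its interaction with intervention is not estimable for the same reason.

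**The case against.** The strongest reply is that the protocol answers the point in its next sentence by promising to control for baseline, and that the SAP fits models with baseline terms. Much of this stands. If baseline vaccination status is among those terms, the intervention odds ratio is not diluted and equals the restricted one. A reader might infer that every planned analysis of vaccination is diluted, or that separation defeats adjustment; the fits above support neither. Separation spoils only the covariate's own coefficient and its interaction with intervention. What the reply does not settle is that neither document names the covariate, and that the SAP's stated first-stage comparison is unadjusted.

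A second reply is that the outcome is undefined. This also stands. A reader might take it as fact that vaccinated people count as successes in every arm. That assumes an ever-vaccinated score, which the documents do not give. If adherence means up to date or a further dose, status can change and previously vaccinated people can still gain or lose it. The surveys that might settle the scoring are attachments not included in the text.

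A reader might also infer that a combined adherence score would be diluted. The documents specify no such score, so that cannot be judged.

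**Conclusion.** The point holds conditionally. Vaccination is a named outcome, eligibility does not select on it, and nothing in either document limits the crude comparison to people who can still be vaccinated. Under an ever-vaccinated score, or any dose already held, the crude risk difference is reduced by exactly 1 − v and the odds ratio moves toward 1. The assumed scenarios make the loss large: crude power of 15% to 55%, against 57% to 96% restricted, for v from 80% down to 40%. Baseline coverage, uptake and absence of dropout are all assumptions, so these figures show the range and do not predict the trial's result.

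The defect is an unspecified outcome and an uncommitted covariate. It is not a demonstrated bias in every vaccination analysis, and it does not reach testing, distancing, hand-washing or mask-wearing. The plan should be amended on this point.

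**What to change.** In the SAP:

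1. Define the vaccination outcome as newly receiving a stated dose by a stated time point.
2. Make the main vaccination contrast the one among participants who did not hold that dose at baseline. For second-stage contrasts, use status at the second randomisation.
3. Alternatively, keep everyone and name baseline vaccination status as a covariate, which gives the same intervention effect. In that case, do not report Wald tests of that covariate or of its interaction with intervention, because separation makes them non-estimable.
4. Report the share already vaccinated at baseline by arm.

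The cost is a few lines of SAP text. The restriction uses a variable fixed before the relevant randomisation, so the randomised comparison is preserved. The estimate will apply only to people not yet holding the dose. The fix also requires that the baseline survey records vaccination status, which cannot be checked from the documents; the second-stage restriction needs the same record at the second randomisation.
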